**NCT# 04552132**

**May 2, 2022**

## Pain Assessment Protocol

This study protocol was approved by the Institutional Review Board of Saint Louis University, Saint Louis, MO (Protocol Number 31359). Patients were recruited for this study from the patients seen at the Center for Advanced Dental Education at Saint Louis University from September 2020 through March 2022. Informed consent was obtained from each patient for participation in this study. The following inclusion criteria were utilized for participation in the study: adults fully able to provide informed consent, with restorable, symptomatic molar teeth (reporting  $\geq 20$ mm on the VAS during the previous 24 hours) seeking endodontic therapy. Patients where both Ibuprofen and Acetaminophen were contraindicated, patients with chronic pain issues for which they regularly need to consume analgesics, and patients having taken analgesics or antibiotics within the previous 6 hours were excluded from this study.

The first patient treated in the study was randomized by coin toss, followed by an alternating pattern thereafter for the 2 groups: GentleWave (GWS) (n=16) or EndoActivator (EA) (n=17). Prior to their clinical evaluation, the patients marked on: 1) a 100mm VAS instrument where they felt best represented their degree of pain experienced at that moment, and 2) a 2nd 100mm VAS instrument their maximum level of pain during the previous 24 hours. Clinical evaluation of the patient included percussion and palpation testing, periodontal probing measurements, thermal pulp sensibility testing using a cold source (Endo Ice), and an evaluation of tooth mobility. Radiographic examination (XDR Radiology, Los Angeles, CA) included bitewing, straight-on periapical, angled periapical, and 4X4 cm high-resolution limited field of view cone beam computed tomography (CBCT) (CAREstream 9600-CAREstream Dental, Atlanta, GA) imaging.

Following the administration of topical anesthetic (20% Benzocaine), the same high-level of anesthetic was administered to all patients, in order to standardize the number of injections received by the participants. If supplemental anesthesia was required, intrapulpal injections were performed for vital teeth and periodontal ligament injections were performed for necrotic teeth.

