Rubber dam isolation and the surgical operating microscope were used throughout the treatment procedure. All deficient existing restorations and caries were removed. If inadequate isolation existed to perform the root canal treatment within an isolated environment, SoundSeal (Sonendo Inc., Laguna Hills, CA), a light-cured composite resin, was used to facilitate proper isolation.

Canal patency was achieved, and working length (WL) was determined using a #10 C-file and Root ZX II electronic apex locator (EAL) (J. Morita USA, Irvine, CA). WL was defined as being 1mm short of full tone on the EAL for patients in the GWS group (per the recommended Sonendo protocol) and 0.5mm short of full tone on the EAL for the EA group. All canals were instrumented to a size #20/.06 Vortex Blue nickel titanium rotary file (DENTSPLY Tulsa Dental Specialties, Tulsa, OK). 5.25% sodium hypochlorite (NaOCl) was administered using a 30-gauge, side-vented needle (ProRinse Probes-DENTSPLY Tulsa Dental Specialties, Tulsa, OK) with each successive file placed into the canal.

For the GWS group, 70% isopropyl alcohol placed on a dry cotton pellet was used to clean and dry the tooth. After having created a suitable platform using SoundSeal, the choice of

GWS cycle was determined according to the clinical situation and the corresponding manufacturer-recommended protocol  (Fig 1).

**Fig 1.** GentleWave System Cycles

Case Type	3% NaOCl	Distilled Water	8% EDTA	Distilled Water
Necrotic	4 Minutes	30 Seconds	1.5 Minutes	15 Seconds
Vital	5 Minutes	30 Seconds	2 Minutes	15 Seconds
Extended	5 Minutes	30 Seconds	2 Minutes	15 Seconds
Low	0.5% NaOCl	Distilled Water	8% EDTA	Distilled Water
	8 Minutes	30 Seconds	2 Minutes	15 Seconds

Settings were chosen based off of the proximity of root apices to vital structures such as the inferior alveolar nerve or maxillary sinus: 'Extended'>2mm, 'Necrotic' or 'Vital' 1-2mm, 'Low'<1mm

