#### Pain Assessment Statistical Analysis

Data was compiled and analyzed by a biostatistician at two different time periods. Therefore, participants that were seen between 09/2020-06/2021 were analyzed separately from those seen between 07/2021-03/2022. Data points for pain assessment and analgesic intake were plotted for visualization. A Shapiro-Wilk test of normality indicated a non-normal distribution of the pain data. Due to the skewness observed, a non-parametric analysis was utilized.

The level of pain recorded from each postoperative VAS was compared to the patient's preoperative VAS score to determine if their pain level had increased or decreased. A two-sided Fischer's Exact Test for Count Data was then used to determine whether postoperative pain decreased relative to preoperative pain scores more often in one group as compared to the other group.

Results were considered significant if the  $p \leq 0.05$ .

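### The planned pain test does not adjust for pulp status at baseline, so a vital/necrotic imbalance between the arms would go uncorrected

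*Combined protocol and SAP*

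**What the plan says.** **Analysis.** Each postoperative VAS is "compared to the patient's preoperative VAS score to determine if their pain level had increased or decreased". The stated purpose of the arm comparison is this: "determine whether postoperative pain decreased relative to preoperative pain scores more often in one group as compared to the other group". The section names the test as follows: "A two-sided Fischer's Exact Test for Count Data was then used". It names no stratum or covariate; the preoperative score enters only through the definition of the endpoint. The same section says that patients seen up to June 2021 and patients seen from July 2021 were analysed separately. It does not give the size of either cohort.

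**Allocation.** In the Pain Assessment Protocol section the first patient was "randomized by coin toss, followed by an alternating pattern thereafter for the 2 groups". The arm sizes are given there as "GentleWave (GWS) (n=16) or EndoActivator (EA) (n=17". No stratification is described.

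**Pulp status.** The clinical evaluation includes "thermal pulp sensibility testing using a cold source (Endo Ice". Where extra anaesthesia was needed, "intrapulpal injections were performed for vital teeth and periodontal ligament injections were performed for necrotic teeth". Fig 1 has separate Vital and Necrotic rows for the GentleWave cycle. The note beneath it selects settings by distance of the apices from vital structures: "Extended'>2mm, 'Necrotic' or 'Vital' 1-2mm, 'Low'<1mm".

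**The concern.** The protocol distinguishes vital from necrotic teeth, and the information comes from the pretreatment examination. If the two kinds of tooth differ in how often pain falls after treatment, an unequal mix between the arms shifts the crude comparison, and the Fisher test attributes that shift to the device. With 16 v 17 patients an unequal mix is quite possible. Strict alternation makes the next assignment predictable, so selection could add to chance. A stratified analysis would remove the shift and might recover some power, without any new data collection.

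**Working it through.** The documents give no power, event rate, effect size or sample-size calculation, so there is no stated figure to reproduce.

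**Inputs from the documents:** 16 v 17 patients; unstratified alternation; two-sided Fisher test at 0.05; two cohorts tested separately.

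**Assumptions, none from the documents:** 50% vital teeth (30% and 70% also tried); average control success rate (pain decreased) of 50%; common odds ratio of 6 or 9 in both strata; vital-necrotic difference in success rate of 0, 20, 40 or 60 points; cohort sizes of 8 v 8 or 8 v 9. Imbalance is treated as chance, although allocation was by alternation.

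**1. How likely is imbalance?** Let X and Y be the numbers of vital teeth in the arms, independent binomials with common probability π.

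- SD of X/16 − Y/17 = √[π(1−π)(1/16 + 1/17)]. At π = 0.5 this is √(0.25 × 0.1213) = 0.174, about 17 points.
- P(|X/16 − Y/17| ≥ t), by exact enumeration at π = 0.5: 29.5% for 20 points, 16.3% for 25 points, 8.0% for 30 points.
- At π = 0.3 or 0.7: 21.8% for 20 points, 5.7% for 30 points.
- In an 8 v 8 cohort at π = 0.5: 45.4% for 20 points, 21.0% for 30 points.

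**2. What would an imbalance do?** The spurious arm difference is imbalance × prognostic difference. For example, 0.30 × 40 = 12 points and 0.30 × 60 = 18 points. There were 20,000 simulated null trials per scenario at 16 v 17. Among those with an imbalance of at least 30 points, the rejection rates were:

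| Prognostic difference | Fisher | Stratified exact |
|---|---|---|
| 0 points | 2.7% | 2.0% |
| 20 points | 5.2% | 3.2% |
| 40 points | 10.4% | 3.1% |
| 60 points | 16.5% | 2.5% |

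Over all null trials, Fisher rejected in 3.3% to 3.5%. Its overall type I error therefore stays below 5%.

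**3. What does stratifying gain for the planned endpoint?** Power at 16 v 17, Fisher to stratified exact test:

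| Prognostic difference | Odds ratio 9 | Odds ratio 6 |
|---|---|---|
| 0 points | 64.2% to 64.4% (+0.2) | 50.8% to 51.2% (+0.4) |
| 20 points | 62.8% to 64.2% (+1.4) | 47.5% to 49.1% (+1.6) |
| 40 points | 56.3% to 61.9% (+5.6) | 41.8% to 46.8% (+5.0) |
| 60 points | 43.8% to 56.0% (+12.2) | 30.3% to 39.6% (+9.3) |

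**4. How does this compare with splitting the cohorts?** Fisher power at 90% v 50% success is 64.7% with 16 v 17, 31.6% with 8 v 9 and 21.7% with 8 v 8. Splitting therefore costs 64.7 − 31.6 = 33.1 to 64.7 − 21.7 = 43.0 points in each analysis. That is well above anything lost by omitting pulp status.

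**The case against.** The case against making this change has several parts.

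- **Prognosis is assumed.** A reader might infer that the plan certainly loses power. The documents do not support that: they say nothing about whether pulp status predicts postoperative pain, or what share of teeth was vital. This stands. With a weak or moderate effect the gain is 2 points or less.
- **Imbalance is possible, not likely.** A 29.5% chance of 20 points or more does not support calling a sizeable imbalance likely. Nor is the Fisher test invalid, since its overall type I error is not inflated. Both points stand; the harm is conditional.
- **Larger power gains come from a different comparison.** Simulating Mann-Whitney against van Elteren on raw VAS (20 mm arm difference, within-stratum SD 20 mm) gives gains of about 7 points for a 20 mm pulp effect (68% to 75%) and 17 points for 30 mm (56% to 73%). Neither test is the planned one, and the plan has no single test of all 33 patients, so these figures do not measure the plan's loss.
- **Stratifying can cost power.** This holds for van Elteren. With no pulp effect it loses about 3 to 4 points at 16 v 17, and at an assumed 8 v 8 it falls from 43% to 37%. It does not hold on average for the stratified exact test, which matched Fisher at 16 v 17 and was slightly better at 8 v 8 (21.5% to 24.4% at odds ratio 9, no pulp effect). In the few trials with an imbalance of at least 30 points and no pulp effect, the stratified exact test did give up about 4 points (62.4% to 58.1%).
- **Pulp status changes treatment only in places.** A reader might infer that vital and necrotic teeth were managed differently throughout. The injection rule applies only when supplementation was needed. By the note under Fig 1, the Vital and Necrotic cycles apply only in the GentleWave arm at 1-2 mm. The EndoActivator regimen is the same for all teeth. This stands.
- **The stratum is not defined.** The protocol lists a cold test, but gives no rule that turns its results into vital or necrotic. This stands, and the fix must supply one.

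**Conclusion.** The concern holds in a limited form. The pain test has no adjustment for a baseline characteristic assessed before treatment, and unstratified alternation gives no protection, so any vital/necrotic imbalance passes straight into the arm comparison. With half the teeth vital, an imbalance of at least 20 points has a 29.5% chance at 16 v 17 and about 45% in an assumed 8 v 8 cohort. Whether that biases the result of this trial depends on the imbalance that occurred and on the prognostic strength of pulp status, and the documents report neither. The change is worth making because it is cheap and the exact stratified test costs no power on average. It does not show that the planned test is invalid or materially underpowered for this reason; separate analysis of the cohorts is the larger cause of lost power.

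**What to change.** 1. Tabulate baseline pulp status by arm, overall and by calendar cohort. State the rule that classifies a tooth as vital or necrotic, using pretreatment findings only.
2. In one analysis pooling both calendar cohorts, replace the crude Fisher test at each time point with an exact Cochran-Mantel-Haenszel test stratified by baseline pulp status. Alternatively, use a rank ANCOVA of postoperative VAS on arm, with preoperative VAS and pulp status as covariates, and state which of the two preoperative VAS readings is used. Prefer either to van Elteren.
3. Stratify by baseline pulp status and not by GentleWave cycle, which is chosen after allocation and belongs to that arm's treatment.
4. Recruitment ended in March 2022, so report this as a post hoc analysis beside the Fisher result.

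The cost is analysis wording, code and a classification rule. No further patient data should be needed, provided that the cold-test findings were kept for each patient.

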Prior to leaving the clinic, the patient was provided an 8.5X11 inch, pre-stamped envelope containing 4 blank VAS forms to be filled out by the patient at 24 hours, 48 hours, 72 hours, and 96 hours postoperatively, as well as 4-days' worth of Ibuprofen (600mg Ibuprofen X 16 tablets) (Ascend Laboratories, LLC, Parsippany, NJ) and Acetaminophen (650mg Acetaminophen X 16 tablets) (Perrigo, Allegan, MI). The printed patient instructions were to take 1 tablet of Ibuprofen every 6 hours as needed for pain. If the Ibuprofen did not provide adequate pain relief, then the patient was instructed to also take 1 tablet of Acetaminophen every 6 hours as needed for pain. If the patient maximized the Ibuprofen and Acetaminophen intake and still required additional pain relief, then patient was instructed to call the clinic and a prescription would be provided for Tramadol 50mg X 12 tabs, to be taken every 6 hours as needed for pain. The patients were provided with a Pain Pill Log to record what analgesics were

taken at what times. After ninety-six hours postoperatively, patients were instructed to mail, or physically return, back to the clinic the large envelope with the 4 completed VAS forms, the Pain Pill Log, as well as any unused analgesics. Patients who properly returned all of the requested paperwork were compensated with a \$75 Visa gift card.

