#### CBCT Healing Assessment and statistical analysis

Patients (GWS=12, EA=14), were recalled at 12 months postoperative, and the same imaging and clinical endodontic testing was done as had been performed preoperatively. A 3-D volumetric analysis using ITK Snap software (ITK SNAP, Philadelphia, PA) was completed

to measure the volume of pre-and-post-operative periapical findings in mm^3. Each individual root was then assigned a 3Droot classification of either healed (normal PDL around the root at recall), healing (reduced size of finding), or diseased (same or larger size finding). Pearson's Chi squared test was used to evaluate if there was any difference in 3Droot healing outcomes between the GWS and EA groups. Results were considered significant if the p≤.05.

Clinical tooth healing classification based on clinical examination and patient report (Ctooth)

Teeth were classified as being clinically successful if the patient had no symptoms other than mild tenderness to percussion. Teeth were not considered as failures due to mild percussion sensitivity alone, as long as the patient reported no pain when chewing.

Pearson's Chi squared test was used to evaluate if there was any difference in Ctooth healing outcomes between the GWS and EA groups. Results were considered significant if the p≤.05.

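### Every pain and healing comparison is judged at p≤0.05 with no primary test, order or adjustment, and the pain data are split by compilation date

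*Combined protocol and SAP*

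**What the plan says.** The Pain Assessment Protocol section gives each patient "4 blank VAS forms to be filled out by the patient at 24 hours, 48 hours, 72 hours, and 96 hours postoperatively". It allocates 16 patients to GentleWave and 17 to EndoActivator.

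The Pain Assessment Statistical Analysis section explains that the data were compiled at two times and that, for this reason, "participants that were seen between 09/2020-06/2021 were analyzed separately from those seen between 07/2021-03/2022". It then says "The level of pain recorded from each postoperative VAS was compared to" the preoperative score, to classify pain as increased or decreased. "A two-sided Fischer's Exact Test for Count Data was then used" to compare the groups on how often pain had decreased. The section ends with its decision rule: "Results were considered significant if the" p-value is 0.05 or less.

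The CBCT Healing Assessment and statistical analysis section covers 12 and 14 recalled patients. It adds a Pearson chi-squared test for the "difference in 3Droot healing outcomes between the GWS and EA groups" and a second one for Ctooth. Each carries its own rule: "Results were considered significant if the p≤.05".

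The threshold is therefore stated three times. No section names a primary outcome or time point, a testing order, an adjustment, or a way to combine the two periods. No test is labelled exploratory.

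**The concern.** When several tests are each allowed to produce a significant result at 0.05 and none is named as the one that answers the question, the chance that at least one is falsely positive can exceed the 5% a reader would assume. A reader also cannot tell whether a reported time point or period was chosen before or after the results were seen.

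The period split adds a second difficulty. The only reason given for it is when the data were compiled. It cuts each pain test to roughly 8 patients per arm (assumed, since counts by period are not given), and the plan has no rule for what to conclude if the two periods disagree.

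**Working it through.** **Inputs from the plan.** Four VAS times, two periods, 16 v 17 patients, a two-sided Fisher test for pain, two Pearson tests at 12 months (12 v 14), and p≤0.05 throughout. The plan states no error rate, so there is no figure of its own to reproduce.

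**Assumed inputs.** Period sizes of 8 v 8 and 8 v 9, with 10 v 10 and 6 v 7 as an alternative; correlation of 0 to 0.8 between a patient's four VAS times; and the proportion whose pain decreased, taken as constant over the four days.

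**Step 1: number of tests.** 4 × 2 = 8 pain tests, plus 2 healing tests, makes 10. Other readings are:
- one Fisher test per period: 2 + 2 = 4
- periods pooled: 4 + 2 = 6
- both preoperative VAS scores used as baseline: 16 + 2 = 18

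**Step 2: nominal rate.** For k independent tests at exactly 5%, the rate is 1 − 0.95^k. This gives 18.5% for 4 tests, 26.5% for 6, 40.1% for 10 and 60.3% for 18. These figures are too high for this plan, for the reasons in Steps 3 and 4.

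**Step 3: true size of Fisher's test.** By exact enumeration the size is at most 2.1% at 8 v 8 and 3.4% at 8 v 9, whatever the improvement rate. With uncorrelated times, the largest rate for the eight tests is 1 − 0.979^4 × 0.966^4 = 1 − 0.919 × 0.871 = 20.0%.

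**Step 4: eight pain tests by simulation.** 20,000 trials per setting with no true difference. The last column adds two independent healing tests at 5% each, using 1 − (1 − F) × 0.95², where F is the rate in the second column.

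| Patients improving | Eight pain tests, 8 v 8 and 8 v 9 | Eight pain tests, 10 v 10 and 6 v 7 | Ten tests, 8 v 8 and 8 v 9 |
|---|---|---|---|
| 50% | 16-20% | 11-14% | 24-28% |
| 70% | 12-15% | 8-10% | 21-23% |
| 80% | 6-8% | about 5% | 15-17% |
| 85% | 3-4% | not tabulated | 12-13% |
| 90% | about 1% | not tabulated | about 11% |

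Examples of the last column: 1 − 0.80 × 0.9025 = 27.8% and 1 − 0.99 × 0.9025 = 10.7%. The two healing tests alone contribute 1 − 0.9025 = 9.75%.

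**Step 5: is 5% fair for the Pearson tests?** At 12 v 14, the size for Ctooth is 4.0-6.6% when 50-90% of teeth succeed. For 3Droot it is about 5% if roots are independent, and about 11% if roots of the same tooth have a correlation of 0.5 (2-3 roots per tooth assumed). Simulating all ten tests with an assumed Ctooth success rate of 85%, instead of fixing the Pearson tests at 5%, gives 11-33%. In an extreme corner (90% improve, 95% Ctooth success) the total is only about 6-7%.

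**Step 6: does pooling alone cure it?** No. With 16 v 17, the four pooled pain tests give 9-10% at 85% improving and about 6% at 90%, both higher than with the split. The six pooled tests together give 15-22%.

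**The case against.** The strongest reply has four parts.

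- **The count is inferred.** The pain section describes Fisher's test in the singular and does not say that it was run once per VAS time. This stands: ten is the natural reading, not a stated number. The conclusion does not hinge on it, because six tests also exceed 5%.
- **Fisher's test is conservative here.** This stands at every improvement rate. A reader might infer a 40% false-positive rate from ten tests at 0.05; the documents do not support that, because the small groups and the correlated times bring it well down.
- **Pain and healing need not share one error budget.** Healing has its own section, its own recalled cohort and different outcomes. This is a fair judgement. If the families are kept apart, the pain tests are below 5% once about 85% of patients improve, under the assumed 8 v 8 and 8 v 9 split. The total of about 11% in the most favourable row comes almost wholly from the two healing tests.
- **The period split is not always the culprit.** This stands too. At high improvement rates the split lowers the false-positive rate, because Fisher's test can hardly reject in such small groups. The case against the split is the lost information and the missing rule for disagreement, not that it always inflates error.

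It might also be said that multiplicity matters little in a small study. The documents, however, neither call the study a pilot nor call the tests exploratory; if that is the intent, saying so is one of the remedies.

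**Conclusion.** The point holds in a limited form. The plan applies p≤0.05 to every comparison with no primary test, order or adjustment, so it does not hold the overall false-positive rate at 5%. The size depends on quantities the plan does not give. For the pain tests alone it runs from about 1% (90% improving) to 16-20% (50% improving), and is lower at 50-80% improving under the 10 v 10 and 6 v 7 split. With both healing tests in the family it is about 11-28%. Period sizes, improvement rates and correlations are all assumptions.

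Two stronger inferences are not supported. One is that the error is far above 5% in every case; high improvement rates contradict this for the pain tests taken alone. The other is that a favourable time point or period was actually selected; the documents show only that nothing in the plan would prevent it.

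**What to change.** 1. Analyse all 33 patients together at each VAS time with period as a stratum, for example by an exact stratified test. Drop the separate period tests as claims of significance; period results can be shown descriptively.
2. State how many tests are run. Then either apply Holm's adjustment across the four VAS times and the two healing outcomes (the smallest of six p-values is compared with 0.05/6 = 0.0083), or label all p-values descriptive. Pooling without this step is not enough.
3. Use a single primary time point only if it was fixed before analysis, and say where. The statistical section is in the past tense and reports pain data already tested for normality, so a time point named now must be disclosed as post hoc; it cannot restore 5% control.

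The cost is a modest reanalysis with no new data. Under Holm, individual results need smaller p-values to be called significant.
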